#### **5.3.7 12-Month Follow-up Visit**

This visit should be conducted in-clinic 12 months ( $\pm 60$  days) post-permanent implant

Subjects with a permanent implant will be evaluated 12 months after initial permanent system implant. In case the subject requires reprogramming, it should be performed before the printout of the current programming parameters record and prior to any study visit assessments. During the visit, the following evaluations and procedures will be performed.

- Occupational/life style information
- NRS, PGIC, patient satisfaction, patient reported pain relief, battery usage
- Other Patient Reported Outcome Measures (EQ5D questionnaire, PCS, STAI, PHQ9, TSK, MOS sleep scale, PROMIS physical function scale, Pain Location, Stimulation Assessment)
- Programming information and program usage including programming parameters record
- Chronic Pain related medication usage
- Adverse events (if applicable)
- Deviations (if applicable)
- Withdrawal (if applicable)
- MRI information (if applicable)
- Death (if applicable)

#### **5.3.8 18-Month Follow-up Visit**

This visit should be conducted in-clinic 18 months ( $\pm 60$  days) post-permanent implant

Subjects with a permanent implant will be evaluated 18 months after initial permanent system implant. In case the subject requires reprogramming, it should be performed before the printout of the current programming parameters record and prior to any study visit assessments. During the visit, the following evaluations and procedures will be performed.

- Occupational/life style information
- NRS, PGIC, patient satisfaction, patient reported pain relief
- Other Patient Reported Outcome Measures (EQ5D questionnaire, PCS, STAI, PHQ9, TSK, MOS sleep scale, PROMIS physical function scale, Pain Location, Stimulation Assessment)
- Programming information and program usage including programming parameters record
- Chronic Pain related medication usage
- Adverse Events (if applicable)
- Deviations (if applicable)
- Withdrawal (if applicable)
- MRI information (if applicable)
- Death (if applicable)

#### **5.3.9 24-Month Follow-up Visit**

This visit should be conducted in-clinic 24 months +/- 60 days post-permanent implant

Subjects with a permanent implant will be evaluated 24 months after initial permanent system implant. In case the subject requires reprogramming, it should be performed before the printout of the current programming parameters record and prior to any study visit assessments. During the visit, the following evaluations and procedures will be performed.

- Occupational/life style information
- NRS, PGIC, patient satisfaction, patient reported pain relief
- Other Patient Reported Outcome Measures (EQ5D questionnaire, PCS, STAI, PHQ9, TSK, MOS sleep scale, PROMIS physical function scale, Pain Location, Stimulation Assessment)
- Programming information and program usage including programming parameters record
- Chronic Pain related medication usage
- Subject study completion
- Adverse Events (if applicable)
- Deviations (if applicable)
- Withdrawal (if applicable)
- MRI information (if applicable)
- Death (if applicable)

#### **5.3.10 MRI information (if applicable)**

An MRI procedure is not indicated as part of this clinical investigation. If an MRI is performed as part of standard practice after permanent device implant, details related to the MRI parameters, device functionality, and adverse events will be collected to evaluate the safety of the SCS device. Note: Guidelines for performing an MRI are contained in the MRI Procedure Information Clinician's Manual for compatible devices.

#### **5.3.11 Death (if applicable), Revisions, Replacements or Explants (Additional Surgery)**

The subject and the implanting physician will collectively make the decision about any possible revision, replacement or explant of the device based upon what is medically safe, what is desired by the subject and what is in the subject's best medical interests. The following information will be collected only for revisions, replacements or explants that occur after the initial permanent procedure:

- Permanent implant and system information (including accessories)
- Reason for revision, replacement or explant
- Adverse Events (if applicable)
- Deviations (if applicable)
- Withdrawal (if applicable)
- Death (if applicable)

If the device is explanted for any reason, and re-implantation is not an option, the subject will be withdrawn from the study. Subjects who undergo a revision or replacement procedure will resume their previous follow-up schedule.

### **5.4 Patient Reported Outcome (PRO) Measures**

The Study Coordinator or designee will give the subject questionnaires to complete on his or her own or apply an interview technique. It is important that the subject understands the meaning of all the words in the questionnaires. The subject should be instructed to ask any questions about the questionnaires if further explanation is needed. Once the subject has completed the questionnaire, the Study Coordinator or designee will review the questionnaire for completeness to verify that all questions have been answered and only one response is chosen for each question unless otherwise noted.

The questionnaires to be completed by the subject will have to be administered in this order;

1. EuroQol 5- Dimensions Questionnaire (EQ5D)
2. Pain Catastrophizing Scale (PCS)
3. State-Trait Anxiety Inventory for Adults (STAI)
4. Patient Health Questionnaire-9 (PHQ9)
5. Tampa Scale for Kinesiophobia (TSK)
6. Medical Outcome Study (MOS) Sleep Scale

7. Patient-Reported Outcome Measure Information System (PROMIS) Physical Function (if available in the country)

The following PRO measures will be collected according to the study requirements.

#### **5.4.1 EuroQol 5- Dimensions Questionnaire (EQ5D) (EuroQol Group, 2009)**

EQ5D is a standardized instrument for use as a measure of health outcome applicable to a wide range of health conditions and treatments. It provides a simple descriptive profile and a single index value for health status. The EQ5D-3L descriptive system comprises the following 5 dimensions: mobility, self-care, usual activities, pain/discomfort and anxiety/depression. Each dimension has 3 levels: no problems, some problems, extreme problems. A visual analog scale (VAS) for health is also included in the measure as a patient-reported estimate of overall health status.

#### **5.4.2 Pain Catastrophizing Scale (PCS) (Sullivan, Bishop, & Pivik, 1995)**

The PCS is a validated scale that measures the magnitude of catastrophizing (negative thoughts and feelings while a patient is experiencing pain). Subjects answer questions about how they feel and what they think about when they are in pain (i.e., not at the current moment). The scale includes 13 statements concerning pain experiences that are rated on a scale between 0 'not at all' and 4 'always'. The scale is self-administered and takes 5 minutes to complete. A higher score indicates a higher level of catastrophizing.

#### **5.4.3 State-Trait Anxiety Inventory for Adults (Spielberger, 1968)**

The State-Trait Anxiety inventory is a self-administered screening for anxiety. Subjects respond to 40 items rated on a scale from 0 to 4. It clearly differentiates between the temporary condition of "state anxiety" and the more general and long-standing quality of "trait anxiety" by providing a score for each. Higher scores suggest greater levels of anxiety.

#### **5.4.4 Patient Health Questionnaire-9 (PHQ-9) (Spitzer, Williams & Kroenke et. al)**

The PHQ9 is a multipurpose, validated instrument for screening, diagnosing, monitoring and measuring the severity of depression. The questionnaire consists of 9 questions that rate the frequency of the symptoms of depression. A follow up non-scored question screens and assigns weight to the degree to which depressive problems have affected the patient's level of function. The responses range between 4 choices (0=not at all to 3=nearly every day). Higher scores indicate a higher likelihood of major depression.

#### **5.4.5 Tampa Scale for Kinesiophobia (TSK) (Woby et al, 2005)**

The TSK is a 11-item self-report checklist using a 4-point Likert scale that was developed from the original 17-item checklist (Miller, Kopri & Todd, 1991) as a measure of fear or movement or (re)injury. The scale is based on the model of fear avoidance, fear of work related activities, fear of movement and fear of re-injury (Vlaeyen et al., 1995). The TSK has also been linked to elements of catastrophic thinking (Burwinkle et al., 2005). The scale can be useful in measuring unhelpful thoughts and beliefs about pain in people with chronic pain.

#### **5.4.6 Medical Outcome Study (MOS) Sleep Scale (Hays & Stewart, 1992)**

The MOS sleep scale is intended to assess the extent of sleep problems and measures 6 dimensions of sleep, including initiation, maintenance, quantity, adequacy, drowsiness and respiratory impairments. It includes 12 questions with the first question assessing how long it takes the subject to fall asleep. The second question asks how many hours each night the subject slept. The remaining 10 questions have a range of 6 responses from 1="all of the time" to 6="none of the time". The scale is self-administered and validated.

#### **5.4.7 Patient-Reported Outcome Measure Information System (PROMIS) Physical Function – Short Form Version 1.2**

The PROMIS Physical Function short form is an 8-item instrument designed to measure physical capability rather than actual performance of physical activities. The scale measures universal physical function rather than disease-specific impairment and assesses current function rather than function over a specified time period. Each question has five potential response options ranging in value from one to five to give a total score ranging from 8 to 40. Scores are converted into t-scores where the average for the general US population is 50 and the SD is 10. Higher scores indicate better physical function. This questionnaire is not available in all languages (e.g. Finnish); as such, it is only required at sites where a translation is available.

#### **5.4.8 Pain Numerical Rating Score (NRS)**

The pain NRS consists of 1 question that will be asked by interviewing the subjects. Patients will be asked to rate, from 0 (no pain) to 10 (worst imaginable pain), their average pain over the past 24 hours specific to the area(s) of chronic pain being treated. A higher score indicates greater pain intensity.

#### **5.4.9 Pain Location**

Pain Location is assessed using a map of the body that is labelled with different numbered quadrants. The subject is asked via interview to indicate the area he/she is feeling pain.

#### **5.4.10 Stimulation Assessment**

The Stimulation Assessment Form includes questions to identify the sensations experienced when stimulation is used. Subjects identify the intensity and areas of sensations, if experienced. Intensity is rated on a scale of 0 (no feeling) to 10 (very intense). A map of the body is labeled with different numbered quadrants to identify the areas of sensations. The subject will be requested via interview technique to indicate the area he/she is feeling sensations.

#### **5.4.11 Patient Global Impression of Change (PGIC) (Hurst & Bolton, 2004)**

The PGIC is a categorical rating scale used to evaluate the subject's impression of change in his/her condition since the beginning of the study treatment. The subject will be requested to rate their overall change in activity limitations, symptoms, emotions and overall quality of life related to his/her condition on a seven-point categorical scale via an interview technique. The categories are as follows: 1-no change, 2-almost the same, 3-a little better, 4-somewhat better, 5-moderately better, 6-better, and 7-a great deal better. Although this tool does not specify the area of change (e.g., pain, function, quality of life, etc.), it allows for an overall integrated assessment from the prospective of the subject. PGIC values of 6 or 7 are reported to correlate best with actual change (Amirfeyz et al, 2009).

### **5.5 Unscheduled Visits**

An Unscheduled visit is defined as any visit where an active study subject returns to the participating study site for medical care outside of a specified study visit. Examples of unscheduled visits may include subjects returning to the office for a reportable adverse event, medication adjustment, wound check and/or device programming change after the permanent system implant. During the visit, the following evaluations and procedures will be performed:

[figure not shown]
- Reason for unscheduled visit
- Programming information and program usage including programming parameters record (after reprogramming if it occurs)
- Stimulation assessment (after reprogramming if it occurs)
- Adverse Events (if applicable)
- Deviations (if applicable)

- Withdrawal (if applicable)

Following an Unscheduled visit, the subject should be seen for the next scheduled study visit within window.

## 5.6 Study Flow Chart

Figure 3: Study Flow Chart

## Clinical Investigation Plan

Table 2: List of all clinical investigation specific tests and procedures

Visit	Baseline (must be completed minimum 3 days before the trial procedure)	Trial System Implant (within 3-45 days from Baseline)	End of Trial System Evaluation	Permanent System implant procedure	3 Month (3 months +/- 30 days post - permanent implant)	6 Month (6 months +/- 30 days post - permanent implant)	12 Month (12 months +/- 60 days post - permanent implant)	18 Month (18 months +/- 60 days post - permanent implant)	24 Month (24 months +/- 60 days post - permanent implant)	Additional surgery (System Revision, Replacement /Explant)	Unscheduled Visit
Study Activity											
Informed Consent Process	X										
Inclusion/Exclusion criteria	X										
Demographics, Pain History & Primary diagnosis	X										
Occupational/lifestyle information	X				X	X	X	X	X		
NRS	X		X		X	X	X	X	X		
PGIC, patient satisfaction, patient reported pain relief and battery usage					X	X	X	X	X		
EQ5D questionnaire	X					X	X	X	X		
PCS	X				X	X	X	X	X		
STAI	X					X	X	X	X		
PHQ9	X					X	X	X	X		
TSK	X				X	X	X	X	X		
MOS Sleep Scale	X					X	X	X	X		
PROMIS physical function scale	X*					X*	X*	X*	X*		
Pain Location	X				X	X	X	X	X		
Stimulation Assessment					X	X	X	X	X		(X)
Chronic Pain Related Medication	X				X	X	X	X	X		
Implant procedure and system data		X		X						X	
Trial system evaluation conclusion			X								

## Clinical Investigation Plan

Visit	Baseline (must be completed minimum 3 days before the trial procedure)	Trial System Implant (within 3-45 days from Baseline)	End of Trial System Evaluation	Permanent System implant procedure	3 Month (3 months +/- 30 days post - permanent implant)	6 Month (6 months +/- 30 days post - permanent implant)	12 Month (12 months +/- 60 days post - permanent implant)	18 Month (18 months +/- 60 days post - permanent implant)	24 Month (24 months +/- 60 days post - permanent implant)	Additional surgery (System Revision, Replacement/Explant)	Unscheduled Visit
Study Activity											
Programming information and program usage including programming parameters record			X		X	X	X	X	X		(X)
Reason for revision/replacement/explant										X	
Reason for unscheduled visit											X
Adverse Event	(X)	(X)	(X)	(X)	(X)	(X)	(X)	(X)	(X)	(X)	(X)
Deviation	(X)	(X)	(X)	(X)	(X)	(X)	(X)	(X)	(X)	(X)	(X)
Withdrawal	(X)	(X)	(X)	(X)	(X)	(X)	(X)	(X)	(X)	(X)	(X)
MRI evaluation			(X)	(X)	(X)	(X)	(X)	(X)	(X)		(X)
Death	(X)	(X)	(X)	(X)	(X)	(X)	(X)	(X)	(X)	(X)	(X)
Subject study completion									X		

X\* if the translated questionnaire is available in the country

(X) if applicable

## 5.7 Description of Activities Performed by Sponsor Representatives

Trained Sponsor personnel will provide technical expertise and technical guidance on the use of the SCS systems, including training and proctored case coverage.

While Sponsor representatives may perform these activities, the Principal Investigator remains responsible for ensuring all clinical investigation data is collected as required per CIP.

## 5.8 Subject Study Completion

When the subject's participation in the clinical study has been completed, the subject will return to the medical care as per physician's recommendation.

## 5.9 Subject Withdrawal

Respecting the subject's right to withdraw, the Investigator should make all reasonable efforts to retain the subject in the clinical investigation until completion of the clinical investigation. Subjects must be informed about their right to withdraw from the clinical investigation at any time and for any reason without sanction, penalty or loss of benefits to which the subject is otherwise entitled. Withdrawal from the clinical investigation will not jeopardize their future medical care or relationship with the Investigator. Subjects will be requested to specify the reason for the request to withdraw. Reasons for subject's withdrawal include, but are not limited to:

- Subject refuses to continue participating in the study.
- Subject does not meet the inclusion/exclusion criteria
- Subject is deceased (cause must be documented).
- Subject's non-compliance.
- Subject's participation is terminated by the PI or Investigator, although the subject consented, since participation is no longer medically appropriate.
- Subject is 'lost to follow up': Subject does not adhere to the scheduled follow up visits but has not explicitly requested to be withdrawn from the clinical study (this does not apply to missed visits). Site personnel should at all times make all reasonable efforts to locate and communicate with the subject in order to achieve subject compliance to the scheduled follow up visits.

A subject will be considered 'Lost to Follow-up' after 2 consecutive missed visit(s) and a minimum of two unsuccessful phone calls from investigational site personnel to the subject or contact to schedule the next follow-up visit. These two phone calls must be documented in the subject's hospital records. If the subject is deemed lost to follow-up a letter should be sent to the subject's last known address or to the subject's general practitioner (GP) and a copy of the letter must be maintained in the subject's hospital records. This letter serves as a last attempt to bring the patient back into compliance. If the patient does not return to the hospital for the next study visit within 2 weeks after the letter was sent, the subject shall be considered as withdrawn. The date of withdrawal should be the date of the first missed study visit.

When subject withdrawal from the clinical investigation occurs, the subject should be followed up as part of standard care. The status of the subject's condition should be documented at the time of withdrawal.

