### 4.4.1 Inclusion Criteria

1. Subject has chronic, intractable pain of the trunk and/or limbs, including unilateral or bilateral pain associated with the following: failed back surgery syndrome and intractable low back and leg pain.
2. Subject has a score of 6 or higher on the NRS for average pain specific to the area(s) of chronic pain being treated over the past 24 hours at the baseline visit.
3. Subject is considered by the Investigator as a candidate for implantation of a spinal cord stimulator system according to the system Instructions for Use.
4. Subject is 18 years of age or older at the time of enrollment.
5. Subject is willing to cooperate with the study requirements including compliance with the regimen and completion of all study visits.
6. Subject has signed and received a copy of the Ethics Committee/Institutional Review Board (EC/IRB) approved informed consent.

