### **5.3.1 Baseline**

(in clinic, visit must be completed minimum 3 days and max 45 days before the trial system evaluation)

The following activities must occur before any study procedure/visit.

- The Principal Investigator or delegated study personnel is responsible for screening all potential patients to determine patient eligibility for the study.
- If a patient meets all inclusion criteria and does not meet any of the exclusion criteria, he/she is eligible for the study.
- The patient is enrolled in the study when the patient signed the EC/IRB approved Informed Consent form.

Record enrollment information (name of the study, date of consent and Inclusion/Exclusion information) in the hospital records and complete the Baseline CRF electronically preferably within 5 days after enrollment. Notification of enrollment to the Sponsor will take place only when the Sponsor receives the Baseline CRF.

NOTE: As soon as the patient signs the Patient Informed Consent form, all Adverse Device Effects and all Serious Adverse Events need to be reported according to the guidelines mentioned in this CIP (refer to section 8.2).

In case the subject was consented to participate in the study, but does not meet inclusion/exclusion criteria, and was not implanted, the subject should be withdrawn and a withdrawal form must be completed. The patient will resume his/her regular standard of care with his/her physician.

In case the subject was consented to participate in the study and was implanted but does not meet inclusion/exclusion criteria, then this is considered a protocol violation. A protocol deviation form needs to be completed and the Sponsor must be informed. The EC/IRB and Competent Authority (CA), if applicable, should be notified appropriately about any deviations with regards to the violation of inclusion/exclusion criteria.

The following information will be collected at the baseline visit:

- Demographics, Pain History, Pain Primary/Secondary Diagnosis, occupational/lifestyle information
- NRS
- Other Patient Reported Outcome Measures (EQ5D questionnaire, PCS, STAI, PHQ9, TSK, MOS Sleep Scale, PROMIS Physical Function scale, Pain Location).
- Chronic Pain related medication usage
- Adverse Events (if applicable)
- Deviations (if applicable)
- Withdrawal (if applicable)
- Death (if applicable)

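### Section 5.9 can close out implanted subjects before their next visit window opens, and it leaves non-compliance undefined as a withdrawal reason after implant

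*Combined protocol and SAP*

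**What the plan says.** Section 5.9 sets the trigger: "A subject will be considered 'Lost to Follow-up' after 2 consecutive missed visit(s) and a minimum of two unsuccessful phone calls". A letter to the subject or the general practitioner then serves as the last attempt. The closing condition reads "If the patient does not return to the hospital for the next study visit within 2 weeks after the letter was sent", and a subject who meets it counts as withdrawn. No date is set for the letter. On dating, the section says: "The date of withdrawal should be the date of the first missed study visit".

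The same section lists reasons for withdrawal, among them "Subject's non-compliance" and "Subject does not meet the inclusion/exclusion criteria". Neither is defined further or limited to subjects without an implant. After withdrawal the section provides for standard care and a note of the subject's condition, but not for further study outcomes. It also asks investigators to try to keep subjects in the study to its end.

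Section 5.3.1 treats ineligibility in two cases. A subject who is ineligible and not implanted is withdrawn. For one who is ineligible and implanted, "then this is considered a protocol violation. A protocol deviation form needs to be completed", with no instruction to withdraw.

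Table 2 gives windows of 30 days either side at 3 and 6 months and 60 days either side at 12, 18 and 24 months. For the last visit, Section 5.3.9 says: "This visit should be conducted in-clinic 24 months +/- 60 days post-permanent implant".

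**The concern.** A subject who has missed two visits still carries the device, and may come to a later one. A deadline tied to the next visit but ending before that visit can take place turns a gap in the data into permanent loss. The later visits are the plan's evidence on sustained relief, which Sections 1, 2 and 4.1 give as a main reason for the study. Under Section 8.2, withdrawal also ends safety surveillance, while device- and procedure-related events in implanted subjects are a descriptive endpoint (Section 4.3.3). Back-dating means that a subject who missed 3 and 6 months is recorded as withdrawn from about month 3.

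The non-compliance reason is a separate route, and it can operate before 6 months. The study is single-arm, the primary population is subjects with NRS at baseline and 6 months (Section 6.1.1), and imputation is left unspecified (Section 6.1.4). If the subjects withdrawn this way tended to have poorer pain results, the primary mean would look better than it should.

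**Working it through.** **Calendar check.** Inputs: windows from Table 2; 14 days from Section 5.9; one month = 365.25/12 = 30.4375 days. Assumptions: a visit counts as missed once its window has closed, the letter goes out that day, and the return is meant to fall inside the visit window. Section 5.5 supports the last of these, because it sends subjects on to their next scheduled visit within window.

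Shortfall = (next target − half-window) − (second missed target + half-window + 14).

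| Visits missed (months) | Second window closes (day) | Letter + 14 (day) | Next window opens (day) | Shortfall (days) | Later visits at stake |
|---|---|---|---|---|---|
| 3 and 6 | 182.625 + 30 = 212.625 | 226.625 | 365.25 − 60 = 305.25 | 78.625, about 79 | 12, 18, 24 |
| 6 and 12 | 365.25 + 60 = 425.25 | 439.25 | 547.875 − 60 = 487.875 | 48.625, about 49 | 18, 24 |
| 12 and 18 | 547.875 + 60 = 607.875 | 621.875 | 730.5 − 60 = 670.5 | 48.625, about 49 | 24 |
| 18 and 24 | 730.5 + 60 = 790.5 | 804.5 | none | no next visit | none |

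The deadline reaches the next window only if the letter is held back at least about 79, 49 or 49 days. A letter sent on the opening day would still cover only 14 days of a window about 120 days long.

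**Which endpoints the letter rule reaches.** The earliest pair of missed visits after implant is 3 and 6 months. When the rule fires, the 6-month assessment is already missing, so the rule adds nothing to the loss of 6-month outcomes.

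**The plan's own figures (Section 6.3).** 267 × 0.90 × 0.70 = 168.2 implanted; 168.2 × 0.86 = 144.7, stated as 145. Half-width = 1.96 × 3/√145 = 0.488, stated as 0.49. All of these reproduce. Projected losses between implant and 6 months are 168 − 145 = 23. The plan does not say how many would arise from non-compliance, so the share lies anywhere between 0 and 23.

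**Illustration for non-compliance, on assumed values.** Suppose that k of the 168 implanted subjects are withdrawn before 6 months, that all others are measured, and that the mean NRS change of the k is worse by d points. The shift in the observed mean is k/168 × d, in the favourable direction:

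- k = 5, d = 2: 5/168 × 2 = 0.06
- k = 12, d = 2: 12/168 × 2 = 0.14
- k = 23, d = 3: 23/168 × 3 = 0.41 (every projected loss attributed to this route)

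All are below the 0.49 half-width, though that interval reflects sampling error and makes no allowance for selection. With k = 0 there is no shift.

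**The case against.** The strongest reply is that the letter has no fixed date. The calls that precede it are meant to arrange the next visit, so calls and letter close to that visit are a natural reading, and the two weeks could then fall inside the window. Section 5.9 also does not say in terms that the return must be in window. This stands: a reader might infer that the deadline always expires too early, and the text does not support "always".

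The subjects concerned have also missed two visits and not answered at least two calls, so many might never return. This too stands. The visits in the last column of the table are at stake; they are not certain losses.

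A reader might take Section 5.9 to order the withdrawal of implanted ineligible subjects. It does not. Section 5.3.1 handles that case with a deviation form, and the list in Section 5.9 merely omits the distinction.

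A reader might also infer that a subject who switches the stimulator off because it does not help counts as non-compliant. The nearest text is the entry criterion in Section 4.4.1 on willingness to cooperate, "including compliance with the regimen and completion of all study visits". That concerns entry, Section 5.3.4 lets subjects adjust stimulation themselves, and no section sets a minimum use. The difficulty is that non-compliance is undefined, not that it is defined this way.

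Finally, the unspecified imputation and the completer population are analysis questions that rewording Section 5.9 would not settle. That is correct, but fewer avoidable gaps leave less for either to carry.

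**Conclusion.** The point holds in a limited form. With a promptly sent letter, the two-week deadline ends about 79 or 49 days before the next window opens, and after missed 18- and 24-month visits it refers to a visit that does not exist. Its reach is the 12- to 24-month descriptive outcomes, up to three visits per affected subject, and later safety surveillance. These sizes rest on the letter date and on reading the return as an in-window visit.

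It would be tempting to say that the letter rule biases the 6-month result. It cannot, on the understanding that a visit is missed only when its window has closed. Only the undefined non-compliance reason can reach the primary endpoint. Selective loss by that route is possible but not shown: the documents give neither a count nor a difference in outcome, and the shifts of 0.06 to 0.41 are illustrations. The ineligibility reason is a gap in wording to be reconciled with Section 5.3.1. The change is worth making because it is cheap, not because the primary analysis is shown to be wrong.

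**What to change.** In Section 5.9:

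- Remove the two-week deadline. Record each missed visit, attempt contact at every remaining scheduled visit, and assign lost to follow-up only when the 24-month window has closed. Bring the back-dating sentence into line with this.
- State that after permanent implant, non-compliance is recorded as a deviation and the subject stays in outcome follow-up and in the analysis unless consent is withdrawn.
- Cross-refer the ineligibility reason to the two cases in Section 5.3.1.

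In Sections 6.4 and 6.5, extend the timing triggers for the final report and the 12-month interim so that each subject has completed the visit, been discontinued, or passed the close of the visit window. Without this, an uncontactable subject kept open could leave a trigger unmet.

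The cost is a few more contact attempts per missing subject, a later final disposition and a small rewording of the triggers. Care, sample size and the subject's right to withdraw are unchanged.
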